---

## PROTOCOL SYNOPSIS

---

The primary symptoms of GERD in Chinese outpatients in Gastroenterology department: A cross-sectional investigation

---

### Study site(s) and number of subjects planned

One site

---

### Study period

Estimated date of first subject enrolled	Aug 2015
Estimated date of last subject completed	Sep 2018

---

### Study design

Cross-sectional investigation

### Objectives

Primary Objective:	Outcome Measure:
To define the primary symptom of GERD in Chinese outpatients in Gastroenterology department	The primary symptoms of GERD in Chinese outpatients in Gastroenterology department defined by 24-hour impedance-pH monitoring, upper endoscopy or proton pump inhibitor test.

Secondary Objective:	Outcome Measure :

 
1. To investigate the symptom distribution of patients who present with symptoms originated from upper gastrointestinal tract and have pathologic esophageal reflux established by 24-hour impedance-pH monitoring, upper endoscopy, or proton pump inhibitor test.
 
2. To evaluate the life quality of patients with atypical GERD symptoms (symptoms except heartburning and regurgitation)
 
3. To investigate the diagnostic value of proton pump inhibitor trial to diagnose GERD with atypical reflux symptoms
 
4. To investigate the predictive value of Gerd Q to diagnose GERD with atypical reflux symptoms with heartburn or regurgitation
 
	
 
1. The percentage of each symptom of GERD in the symptom questionnaire in Chinese outpatients in Gastroenterology department
 
2. The measurement of SF-36 questionnaire of GERD patients with atypical symptoms before PPI test
 
3. The sensitivity and specificity of positive PPI test in patients with atypical reflux symptom
 
4. The concordance rate of Gerd Q with 24-hour pH monitoring in GERD patients with atypical reflux symptoms with heartburn or regurgitation
 

### **Target subject population**

Consecutive patients aged 18–65 years who go to the gastroenterology clinic presented with upper gastrointestinal discomfort, such as the following symptoms: heartburn, regurgitation, dysphagia, substernal pain, epigastric pain, epigastric burning, early satiety, postprandial fullness.

### **Duration of treatment**

4-8 weeks

### **Investigational product, dosage and mode of administration**

Esomeprazole, 20mg bid, p.o

4-8 weeks

### **Statistical methods**

Assuming the prevalence of GERD is 30%, 400 completed patients provides a precision (half width of 95% CI) of 0.045 for the estimate of two-sided 95% confidence interval of the primary endpoint. All patients underwent upper endoscopy or an ambulatory 24-h pH monitoring. Pathologic esophageal acid reflux was defined as the percentage total time for which a pH value < 4 was >4.2 % in the distal esophagus. Then, patients were treated with esomeprazole 20 mg twice daily for 28 days. The symptom scores were measured by the frequency score multiplied by the severity scores of the predominant symptom before and at the end of the treatment, and the “ PPI test ” was defined as positive if the overall scores of the predominant dyspeptic symptom in the fourth week decreased by >50 % compared with those of the baseline.

Clinical Study Protocol  
Drug Substance Esomeprazole  
Study Code D9612L00157  
Edition 2.0  
Date Jun 8 2018

GERD is defined by either 24-hour impedance-pH monitoring or positive PPI test or positive result from endoscopy. The percentage of each symptom of GERD in the symptom questionnaire in Chinese outpatients in Gastroenterology department will be calculated. The symptom of the highest percentage will be the primary symptom.

	PAGE
TITLE PAGE .....	1
PROTOCOL SYNOPSIS.....	2
TABLE OF CONTENTS.....	5
1. INTRODUCTION .....	7
1.1 Background and rationale for conducting this study .....	7
1.2 Rationale for study design, doses and control groups.....	8
1.3 Study Design .....	9
2. STUDY OBJECTIVES.....	10
2.1 Primary objective .....	10
2.2 Secondary objectives.....	10
2.3 Safety objectives .....	10
3. SUBJECT SELECTION, ENROLMENT, RANDOMISATION, RESTRICTIONS, DISCONTINUATION AND WITHDRAWAL.....	10
3.1 Inclusion criteria .....	11
3.2 Exclusion criteria .....	11
3.3 Subject enrolment and randomization.....	11
3.4 Methods for assigning treatment groups .....	11
3.5 Methods for ensuring blinding.....	11
3.6 Criteria for withdrawal.....	12
3.7 Discontinuation of the study .....	12
4. STUDY PLAN AND TIMING OF PROCEDURES.....	12
4.1 Enrolment/screening period .....	15
4.2 Treatment period.....	15
4.3 Follow-up period.....	15
5. SAFETY REPORTING AND MEDICAL MANAGEMENT .....	15
5.1 Definition.....	15
Adverse Events.....	15
Serious Adverse Event.....	15
Adverse Drug Reaction (ADR) .....	16

5.2	Reporting of Serious Adverse Events.....	16

## **1. INTRODUCTION**

### **1.1 Background and rationale for conducting this study**

Gastroesophageal reflux disease (GERD) is a condition which develops when the reflux of stomach contents cause troublesome symptoms and/or complication. It is one of the most common gastrointestinal diseases in the West countries and imposes a heavy burden on the population. It was reported that the prevalence of GERD has increased greatly since 1995, particularly in North America and East Asia. GERD has been believed to be a major risk factor for esophageal adenocarcinoma, especially in Barrett's esophagus. Thus it is important to confirm the diagnosis of GERD and give the subsequent therapy for the patient to lower down the risk for esophageal adenocarcinoma.

According to the global consensus issued in 2006, GERD could be diagnosed simply by typical reflux symptoms. Heartburn and acid regurgitation are the primary symptoms of gastroesophageal reflux disease. These two symptoms are derived from the studies performed in western countries. And using the 24-hour esophageal pH monitoring as “gold standard”, the sensitivity and specificity of reflux symptoms are moderate. The current prevalence of heartburn and/or regurgitation in China was 6.2% weekly and there is an increasing trend in the prevalence of GERD. It is reported that the prevalence of GERD is much lower in China than that in other western countries.. This might be due to the diet culture in China, where a lower fat intake is introduced. Another common reason is about the understanding of GERD symptoms. The primary symptom of GERD is heartburn as confirmed in the Montreal consensus, which is defined as the burning sensation in the retrosternal area. However, there is no equivalent word for heartburn in Chinese, many Chinese patients came to the hospital with the complaint of “burning in the stomach”, thus the questionnaire which focus on the

heartburn symptoms would underestimate the prevalence of GERD. The last and also the most important reason might lie in that the symptoms which indicate reflux were different in Chinese population. In other words, heartburn might not be the primary reflux symptom in China. For example, more symptoms originated from the upper gastrointestinal tract was described as reflux symptom when patients went to see doctors in China. According to the investigation in our own center, about one third of dyspepsia patients without reflux symptoms presented pathologic esophageal acid reflux in our clinic. Thus heartburn was not understood as well as in other western countries, the symptoms of GERD might distribute differently in China compared to other western countries. So it is necessary to investigate the primary symptoms and spectrum of GERD in Chinese population in order to better define and diagnose GERD.

## **1.2 Rationale for study design, doses and control groups**

The symptom spectrum of GERD has been studied in the western population using the 24-hour esophageal pH monitoring as the gold standard, heartburn and regurgitation has been advocated as the primary symptoms of GERD according to these studies. However, the current studies on GERD in China referred to these western studies and took it for granted that heartburn and regurgitation were also the primary symptoms of GERD. Our clinical practice indicated that a lot of Chinese patients who came to the hospital seeking for therapy of symptoms originated from the upper GI tract including epigastric pain, epigastric burning sensation et al turned out to be GERD. Thus the primary symptoms of GERD might differ from that in the western countries. It is necessary to find out the primary symptoms and symptoms spectrum in Chinese population, which might be useful in our clinical management.

[figure not shown]
All the included patients who do not have positive finding during 24 hour esophageal pH monitoring would be administered with esomeprazole 20mg bid for 4 weeks which would be a complement for GERD diagnosis of pH monitoring.

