### **3.4 Methods for assigning treatment groups**

All the patients who were endoscopy negative, with esophagitis or Barrett's esophagus would be given esomeprazole 20mg bid for 4- 8 weeks.

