## **4. STUDY PLAN AND TIMING OF PROCEDURES**

The study includes screening and treatment period. The screen period would be 7 days, during this stage all the procedure including questionnaires, upper endoscopy and MII-pH monitoring need to be finished. The treatment period would be 4 to 8 weeks according to the findings under upper endoscopy. For patients with esophagitis, this period would be 8 weeks; for patients with normal findings, this period would be 4 weeks.

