### **7.3 Outcome measures for analyses**

Pathologic esophageal acid reflux was defined as the percentage total time for which a pH value < 4 was >4.2 % in the distal esophagus. Then, patients were treated with esomeprazole 20 mg twice daily for 28 days. The symptom scores were measured by the frequency score multiplied by the severity scores of the predominant symptom before and at the end of the treatment, and the “ PPI test ” was defined as positive if the overall scores of the predominant dyspeptic symptom in the fourth week decreased by >50 % compared with those of the baseline. GERD is defined by 24-hour impedance-pH monitoring, upper endoscopy or positive PPI test.

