#### **7.4.2 Analysis of the secondary variable(s)**

The percentage of each symptom of GERD in the symptom questionnaire in Chinese outpatients in Gastroenterology department will be calculated.

The life quality of GERD patients with atypical symptoms before PPI test will be measured via SF-36 questionnaire.

Receiver operating characteristic (ROC) curves will be constructed to identify the sensitivity and specificity of either GERD Q or 4-week PPI test against positive 24-hour pH monitoring or positive endoscopy result in GERD patients with atypical reflux symptoms

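### Section 1.2 ties the PPI test to a negative pH result while 3.4, 4, the synopsis and 7.3 do not; under 1.2, PPI-test sensitivity against the planned reference is not identified

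*Combined protocol and SAP*

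**What the plan says.** The protocol describes the patients who receive esomeprazole, and so have a PPI-test result, in several places.

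- **Section 1.2** conditions on the pH result: "All the included patients who do not have positive finding during 24 hour esophageal pH monitoring would be administered with esomeprazole". It gives the purpose as an add-on to the pH study, "which would be a complement for GERD diagnosis of pH monitoring".
- **Section 3.4** conditions on endoscopy category and not on pH: "All the patients who were endoscopy negative, with esophagitis or Barrett's esophagus would be given esomeprazole 20mg bid for 4- 8 weeks".
- **Section 4** lets endoscopy alone set the duration: "The treatment period would be 4 to 8 weeks according to the findings under upper endoscopy". Tables 1 and 2 divide patients by endoscopy in the same way.
- **Section 7.3**, like the synopsis, places treatment after the pH definition with no pH condition: "Then, patients were treated with esomeprazole 20 mg twice daily for 28 days".

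The analysis that depends on this is secondary outcome 3: "The sensitivity and specificity of positive PPI test in patients with atypical reflux symptom". Section 7.4.2 fixes the reference for it, planning ROC curves for this purpose: "sensitivity and specificity of either GERD Q or 4-week PPI test against positive 24-hour pH monitoring or positive endoscopy result". That analysis is confined to those whose symptoms are atypical.

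**The concern.** Sensitivity is the proportion testing positive among reference-positive patients, so those patients must have taken the test. Under sections 3.4, 4 and 7.3 they do. Under section 1.2 a pH-positive patient falls outside the group named for esomeprazole and has no PPI-test result.

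The result would then be missing by design, and missing according to one component of the reference standard itself. The reference-positive patients left would be those with positive endoscopy and negative pH. There is no reason given to expect them to respond to a PPI as pH-positive patients do, and more recruitment would not repair the gap. At stake is the sensitivity half of secondary outcome 3. There is also a practical risk: with two descriptions in force, pH-positive patients could be handled differently from one to the next.

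**Working it through.** **1. The plan's own figure.** Section 7.1 assumes 30% prevalence and 400 completers, with a 95% half-width of 0.045. Check: 1.96 × √(0.30 × 0.70 / 400) = 0.0449. It reproduces. It concerns the prevalence estimate and does not bear on PPI-test sensitivity, for which the plan gives no precision.

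**2. Who has a PPI-test result.** Assume each patient has both endoscopy and pH monitoring, as section 4 requires.

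| pH | Endoscopy | Reference (7.4.2) | Tested under 3.4 | Tested under 1.2 |
|---|---|---|---|---|
| + | + | positive | yes | no |
| + | − | positive | yes | no |
| − | + | positive | yes | yes |
| − | − | negative | yes | yes |

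Under 1.2, two of the three reference-positive cells are empty. Against pH monitoring alone the sensitivity denominator is zero. Against the composite reference only the third row contributes. The reference-negative row is fully tested under either rule, so specificity is unaffected. GERD Q is a questionnaire score that needs no PPI-test result, so its analysis is unaffected too.

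**3. Size, on assumed inputs.** None of these is given in the documents for this purpose:

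- Reference-positive patients: 0.30 × 400 = 120.
- Sensitivity in the patients tested: 0.70.
- Share *f* of reference-positives who are pH-positive: 50% to 100%.

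If all 120 are tested, the half-width is 1.96 × √(0.70 × 0.30 / 120) = 0.082.

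Under 1.2, the number tested is 120 × (1 − *f*). Full-reference sensitivity equals (1 − *f*) × 0.70 + *f* × (sensitivity in pH-positives). The last term is unobserved and can lie anywhere from 0 to 1, so the bounds are 0.70(1 − *f*) and 0.70(1 − *f*) + *f*.

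| *f* | Tested | Half-width, tested subset only | Bounds on full-reference sensitivity |
|---|---|---|---|
| 50% | 60 | 0.116 | 0.35 to 0.85 |
| 70% | 36 | 0.150 | 0.21 to 0.91 |
| 90% | 12 | 0.259 | 0.07 to 0.97 |
| 100% | 0 | none | 0 to 1 |

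The bounds depend on *f* and not on sample size, and they leave out sampling error. With 80 reference-positives (20% of 400) the half-width with all tested becomes 0.100, but the bounds are the same.

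**4. Limits of these counts.** The 30% in section 7.1 is an assumed GERD prevalence, and section 7.3 lets a positive PPI test alone define GERD. It is neither a pH-positive rate nor a reference-positive rate. Secondary outcome 3 is also confined to patients with atypical symptoms, whose number is not given. The count of 120 and the half-widths are therefore best-case.

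**The case against.** The strongest reply is that section 1.2 is rationale, and the operative text points the other way. Section 3.4 covers the endoscopy categories left after the exclusions, section 4 and both schedule tables follow endoscopy alone, and section 7.3 has no pH condition. Section 3.6 withdraws patients who cannot finish esomeprazole and section 7.2.1 analyses completers, which fits treatment of everyone. On that text the sensitivity analysis is feasible. Section 1.2 could also be read as explaining why a patient with a negative pH study still gets a PPI. A figure just before the sentence in 1.2, and the flow chart in 1.3, are not available to this review and might show the intended flow.

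Much of this stands. A reader might infer that section 1.2 expressly excludes pH-positive patients. It does not: the word *only* is absent, and the restriction is drawn from the condition on pH together with the stated complementary purpose. A reader might also infer that section 7.3 orders treatment for all. It says patients, without *all*; the explicit statement is in 3.4.

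What does not stand is that no correction is needed. The protocol states no rule that one section prevails over another. Section 1.2 names a group, a dose and a duration, so it can be followed as an instruction. The condition on a negative pH finding has little purpose if everyone is treated, and a figure would not remove a conflict between written passages.

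**Conclusion.** The concern holds as an inconsistency with a conditional consequence. The protocol describes two different populations for the PPI test. If section 1.2 is followed, PPI-test sensitivity over the section 7.4.2 reference is not identified without assumptions about untested patients. On the assumed inputs, an estimate with a half-width of about 0.08 is replaced by bounds of 0.35 to 0.85 when half of the reference-positives are pH-positive, and 0.07 to 0.97 when 90% are. The identification problem itself does not rest on those inputs.

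Three stronger conclusions might be drawn, and the documents support none of them:

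- That no sensitivity at all could be computed. Endoscopy-positive, pH-negative patients would still supply a figure, though for a selected subset and not the planned quantity.
- That secondary objective 3 would be wholly unanswerable. Its outcome includes specificity, which survives.
- That the primary objective is damaged. A pH-positive patient already counts as GERD under section 7.3 without a PPI test.

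Confidence is high that the passages differ, and lower about which was intended. It is worth correcting because a planned secondary analysis depends on it.

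**What to change.** Reconcile section 1.2 with section 3.4, section 4, the synopsis and section 7.3, so that one population receiving the PPI test is stated throughout. Which population that is remains a clinical choice for the investigator. Then tie secondary outcome 3 and section 7.4.2 to it:

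- If pH-positive patients receive the PPI test, remove the pH condition from section 1.2. The planned analysis can then stand.
- If they do not, withdraw the PPI-test sensitivity claim from secondary outcome 3 and section 7.4.2, and leave the GERD Q claim in place. Report PPI-test specificity and, clearly labelled as a selected subset, the PPI-test result in endoscopy-positive, pH-negative patients.

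In either case, state the number of reference-positive and reference-negative patients with atypical symptoms who have a PPI-test result, so that the actual denominators are visible.

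The cost is a wording amendment. In the second case one secondary claim is also lost.

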#### Benefit/risk and ethical assessment

The study might be helpful in the understanding of symptom spectrum of GERD in Chinese population and promote the GERD study in China. There won't be any risk and ethical issue in the current study.

### 1.3 Study Design

Figure 1 Study flow chat

## 2. STUDY OBJECTIVES

### 2.1 Primary objective

Primary Objective:	Outcome Measure:
To define the primary symptom of GERD in Chinese outpatients in Gastroenterology department	The primary symptoms of GERD in Chinese outpatients in Gastroenterology department defined by 24-hour impedance-pH monitoring, upper endoscopy or proton pump inhibitor test.

### 2.2 Secondary objectives

Secondary Objective:	Outcome Measure :

 
1. To investigate the symptom distribution of patients who present with symptoms originated from upper gastrointestinal tract and have pathologic esophageal reflux established by 24-hour impedance-pH monitoring, upper endoscopy or proton pump inhibitor test.
 
2. To evaluate the life quality of patients with atypical GERD symptoms (symptoms except heartburning and regurgitation)
 
3. To investigate the diagnostic value of proton pump inhibitor trial to diagnose GERD with atypical reflux symptoms
 
4. To investigate the predictive value of Gerd Q to diagnose GERD with atypical reflux symptoms with heartburn or regurgitation
 
	
 
1. The percentage of each symptom of GERD in the symptom questionnaire in Chinese outpatients in Gastroenterology department
 
2. The measurement of SF-36 questionnaire of GERD patients with atypical symptoms before PPI test
 
3. The sensitivity and specificity of positive PPI test in patients with atypical reflux symptom
 
4. The concordance rate of Gerd Q with 24-hour pH monitoring in GERD patients with atypical reflux symptoms with heartburn or regurgitation
 

### 2.3 Safety objectives

NA

## 3. SUBJECT SELECTION, ENROLMENT, RANDOMISATION, RESTRICTIONS, DISCONTINUATION AND WITHDRAWAL

The study will be done in the outpatient clinic, department of Gastroenterology, first affiliated hospital, sun yet-sen university.

### **3.1 Inclusion criteria**

1. Consecutive patients aged 18–65 years who go to the gastroenterology clinic presented with upper gastrointestinal discomfort, such as the following symptoms: heartburn, regurgitation, dysphagia, substernal pain, epigastric pain, epigastric burning, early satiety, postprandial fullness.
2. The previous symptoms should last for at least 3 months.
3. The frequency of the previous symptoms should be at least 3 days per week with at least moderate.
4. All the previous symptoms would be evaluated in the questionnaires (see attachment).

### **3.2 Exclusion criteria**

1. Patients with gastric or duodenal ulcers, upper GI neoplasms on upper endoscopy
2. Patients with severe cardiac or pulmonary diseases, diabetes or rheumatic diseases
3. Patients with a history of operations in the upper GI tract
4. Patients with renal failure or abnormal liver function
5. Patients with use of non-steroidal anti-inflammatory drugs (NSAIDs)
6. Patients who are allergy to esomeprazole
7. Pregnancy or lactating mother

### **3.3 Subject enrolment and randomization**

Consecutive patients who met the inclusion criteria in the Gastroenterology clinic in the first affiliated hospital will be enrolled in the study. There will not be any randomization in the study.

### **3.4 Methods for assigning treatment groups**

All the patients who were endoscopy negative, with esophagitis or Barrett's esophagus would be given esomeprazole 20mg bid for 4- 8 weeks.

### **3.5 Methods for ensuring blinding**

Not applicable. This is a cross-sectional study.

### **3.6 Criteria for withdrawal**

Patients would be withdraw from the current study if their symptoms do not meet the inclusion criteria, they could no tolerate any procedure of the study, they could not finish the esomeprazole therapy part.

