**Table 1 Study Plan detailing the procedures for patients with esophagitis**

Visit	1	2	3	4	5	6	7
Visit window	Screening						
Days -7 to 0 for Visit 1							
±0 day for Visit 2							
±1 day for Visits 3 and 4							
±5 days starting at Visit 5							
Week		0	1	2	4	8	12
Day	-	0	7	14	28	56	84
Written informed consent (including tissue samples, pharmacogenetics)	X						
Demographics	X						
Physical examination, height, and weight	X						
Medical/surgical history	X						
Inclusion/exclusion criteria	X	X					
Treatment dispensed/returned		X					X
Concomitant medication	X	X	X	X	X	X	X
GERD questionnaire		X	X	X	X	X	X

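### Withdrawal under section 3.6, combined with the completers-only set in 7.2.1, drops patients whose GERD is already established from the primary symptom percentages

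*Combined protocol and SAP*

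**What the plan says.** Section 3.6 (Criteria for withdrawal) removes a patient from the study as a whole in either of these situations: "they could no tolerate any procedure of the study, they could not finish the esomeprazole therapy part". Nothing in the protocol separates stopping a test or the drug from leaving the study, and nothing provides for data collection afterwards.

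The case definition needs one positive criterion only. The synopsis, under Statistical methods, states: "GERD is defined by either 24-hour impedance-pH monitoring or positive PPI test or positive result from endoscopy". Section 7.3 repeats this.

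Section 4 puts the diagnostic work-up into the seven-day screening period: "during this stage all the procedure including questionnaires, upper endoscopy and MII-pH monitoring need to be finished". Treatment follows, and section 3.4 includes patients already positive on endoscopy: "All the patients who were endoscopy negative, with esophagitis or Barrett's esophagus would be given esomeprazole 20mg bid for 4- 8 weeks". On duration, section 4 adds: "For patients with esophagitis, this period would be 8 weeks"; with normal findings it is 4 weeks.

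Section 7.2.1 defines the only analysis set, as patients who complete the study per protocol. Section 7.4.1 computes the percentage of each symptom of GERD and names the highest as the primary symptom.

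In Tables 1 and 2 the row "GERD questionnaire" has its first mark at Visit 2 (Day 0) and none at the screening visit. Inclusion criterion 4 (section 3.1) has the qualifying symptoms evaluated in the questionnaires.

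**The concern.** The primary question is which symptoms GERD patients present with. Answering it takes two things: evidence of GERD and a baseline symptom record. A patient with esophagitis or a positive pH study needs no further step to be a case. Sections 3.6 and 7.2.1 together nevertheless make that patient's contribution depend on tolerating the procedures and finishing weeks of esomeprazole.

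Three things are at stake.

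- **Selection in the primary outcome.** Confirmed cases are lost for reasons unrelated to whether they have GERD. The esophagitis group has to last twice as long, so it is likely to lose more. If erosive and non-erosive patients differ in symptoms, the percentages move.
- **Later data.** Withdrawal ends collection, so a patient who stops in week 2 has no Visit 5 (week 4) score, although that visit is already scheduled.
- **Screening withdrawals.** A patient with esophagitis on endoscopy who then cannot tolerate the pH catheter may be withdrawn before any symptom questionnaire has been completed.

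**Working it through.** **1. The plan's own figure.** Section 7.1 gives a half-width of 0.045 for a prevalence of 30% in 400 completed patients. Check: 1.96 × √(0.30 × 0.70 / 400) = 0.0449, so the figure reproduces. The 400 are completers, and there is no allowance for withdrawal. They would include 0.30 × 400 = 120 GERD cases. For a symptom reported by half of them, the half-width is 1.96 × √(0.50 × 0.50 / 120) = 0.0895, about 9 points.

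**2. What each type of withdrawal loses.**

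| Patient | GERD status known? | Baseline symptoms recorded? | Lost through |
|---|---|---|---|
| Esophagitis, pH catheter not tolerated in screening | Yes (endoscopy) | Unclear: yes if questionnaires precede the procedures; no if first given at Visit 2 | 3.6 and 7.2.1, possibly never collected |
| pH-positive, treated, stops in week 2 | Yes (pH) | Yes (Day 0 at the latest) | Primary analysis: 7.2.1. Visit 5 score: 3.6 |
| Esophagitis, stops in week 6 | Yes (endoscopy) | Yes, and the week-4 score too | Primary analysis: 7.2.1 |

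The third row is the plainest. By week 6 everything the primary analysis and the PPI test need has been collected, yet the patient is withdrawn and is not a completer.

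**3. Unequal hurdle (assumed rates).** The documents give no stopping rate. Assume a constant 2% to 5% per week. The proportion finishing is (1 − rate)^weeks.

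| Rate per week | Finish 4 weeks | Finish 8 weeks | Lost: normal endoscopy | Lost: esophagitis |
|---|---|---|---|---|
| 2% | 0.98⁴ = 0.922 | 0.98⁸ = 0.851 | 8% | 15% |
| 5% | 0.95⁴ = 0.815 | 0.95⁸ = 0.663 | 19% | 34% |

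**4. Effect on a symptom percentage (assumed mix).** Assume one third of GERD cases are erosive, with heartburn in 70% of erosive and 45% of other cases. With no losses: (0.70 + 2 × 0.45) / 3 = 53.3%.

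- At 2% per week: (0.851 × 0.70 + 2 × 0.922 × 0.45) / (0.851 + 2 × 0.922) = 52.9%, a shift of 0.4 points.
- At 5% per week: (0.663 × 0.70 + 2 × 0.815 × 0.45) / (0.663 + 2 × 0.815) = 52.2%, a shift of 1.1 points.

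**5. Stronger selection (assumed).** Step 4 lets patients drop out by endoscopic group only. If withdrawn patients themselves differ, the shift is larger. With a true share of 50%, 20% withdrawn and a share of 30% among them, completers show (0.50 − 0.20 × 0.30) / 0.80 = 55.0%; with 70% among them, 45.0%. At 10% withdrawn the figures are 52.2% and 47.8%. Nothing in the documents indicates a difference of that size.

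**The case against.** The strongest reply is that most of the harm belongs to 7.2.1, not 3.6. For the primary outcome in treated patients this is correct. A reader might infer from 3.6 that the data of esomeprazole stoppers are never collected, so that no change of analysis set could bring them back. The documents do not support that: such patients have had their screening tests and are scheduled for a Day 0 questionnaire. Redefining the set would recover them. What 3.6 itself costs is their later data.

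A reader might also infer that screening withdrawals certainly leave no symptom record. That too goes beyond the text. Section 4 and inclusion criterion 4 place questionnaires in screening. The tables, read from PDF, show no rows for endoscopy, pH monitoring or SF-36, and the questionnaire they list may not be the symptom questionnaire. Loss before the first questionnaire is possible, not established. But neither section 4 nor the tables ensures that the questionnaire comes before the procedures.

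Third, a week-4 score after stopping in week 2 is not the PPI test, which section 7.3 defines after 28 days of esomeprazole. This stands. Such a score can support a sensitivity analysis but cannot replace the missing test result.

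Finally, the plan is inconsistent on who must do what. The synopsis has patients undergo endoscopy or pH monitoring, while section 4 requires both. Section 1.2 gives esomeprazole to patients without a positive pH finding, while section 3.4 is broader. The reference to any procedure in 3.6 could mean any single one or all of them. These places need reconciling, and how often 3.6 would bite depends on the outcome. The esophagitis case does not turn on them: sections 3.4 and 4 give these patients 8 weeks of treatment after a test that already makes them cases.

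**Conclusion.** The point holds in limited form. As written, 3.6 and 7.2.1 together remove confirmed GERD cases from the primary symptom percentages, with an 8-week hurdle for esophagitis against 4 weeks for a normal endoscopy, and 3.6 ends later collection such as the Visit 5 score. Questionnaire timing is contradictory and leaves room for a further loss in screening.

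The size is probably modest: about 1 point or less under the assumed 2-5% weekly stopping and the assumed symptom mix, against a sampling half-width near 9 points. A shift of several points needs withdrawn patients to differ markedly from the rest, which the documents neither show nor exclude. A reader might infer that the choice of primary symptom would change. That is not shown, since no percentage for a competing symptom is given. The case for changing the plan is that the selection is avoidable at little cost.

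**What to change.** - **(a) Sections 3.6 and 7.2.1.** Separate stopping a procedure or the drug from leaving the study. State that a patient with a positive endoscopy or pH result and a baseline symptom questionnaire stays in the primary symptom analysis, whether or not the other test or esomeprazole is completed.
- **(b) Section 4 and Tables 1-2.** State that the symptom questionnaire and SF-36 are completed in screening, before endoscopy and the catheter, and align both tables with section 4.
- **(c) After early stopping.** Unless consent is withdrawn, still collect the scheduled Visit 5 questionnaire, with stop date and reason. Flag it as not a completed 28-day PPI test and use it only in a sensitivity analysis of PPI-test accuracy.

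Treatment is unchanged. The cost is rewording two sections, editing both tables (including an SF-36 row that neither shows) and one follow-up questionnaire for early stoppers. The downside is that some retained patients will lack one reference test or a complete PPI test and must be flagged. Patients negative on both tests who stop early still have no settled GERD status; this change does not resolve that, and they should be counted and reported.
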